## 2.3 Participant disposition, demographics and other baseline characteristics

### 2.3.1 Participant disposition

Safety set will be used for the summary and listing of participant disposition.

The overall number of participants who completed, and discontinued the study will be summarized including the reasons for discontinuation.

Number of participants with protocol deviations will be tabulated by category (e.g., selection criteria not met, subject not withdrawn as per protocol, treatment deviation, prohibited concomitant medication, other) and deviation.

The number of participants included in each analysis set will be tabulated. Participant exclusion from analysis sets will be listed for all participants with reasons for exclusion (i.e. including both protocol and non-protocol deviations).

### 2.3.2 Demographics and other baseline characteristics

Demographic and other baseline data including disease characteristics will be summarized descriptively by study arm based on safety set.

Demographics include age, sex, race, ethnicity, weight, height and Body Mass Index (BMI). For age and BMI, both categorical and continuous summaries will be presented.

The categories for BMI are as follows:

- BMI ( $< 25$ ,  $25 \leq 30$ ,  $\geq 30$ )

Disease related baseline characteristics include:

- Peanut specific IgE/IgG4
- Total IgE/Total IgG4
- Size of wheal diameter (SPT)
- History of allergies to other foods
- History of anaphylactic reaction to peanut

- Age at diagnosis of peanut allergy
- History of peanut desensitization therapy
- Co-morbid allergic diseases (i.e., asthma, allergic rhinitis, atopic dermatitis)

Relevant medical histories and current medical conditions at baseline will be summarized by system organ class and preferred term, by treatment arm. Medical history will be coded with the Medical Dictionary for Regulatory Activities terminology (MedDRA) using the most recent version at the time of database lock.

## **2.4 Treatments (study treatment, rescue medication, concomitant therapies, compliance)**

### **2.4.1 Study treatment / compliance**

The duration of exposure to study drug in days to each study arm will be summarized using descriptive statistics.

Duration of exposure to study treatment will be calculated as the number of days between the first dose date and the last dose date exposed to that treatment over the specified period (Duration of exposure = (date of last known study treatment – date of first known study treatment)).

In addition, the number of doses, total cumulative dose and number of missed doses will be presented. Categorical data (in weeks) will be summarized as frequencies and percentages. For continuous data, mean, standard deviation, median, 25th and 75th percentiles, minimum and maximum will be presented.

Compliance will be calculated as the percentage of the number of days where study drug was administered as per protocol (CCI [REDACTED]) divided by the duration of exposure (i.e., the number of days between first and last dose).

Overall compliance will be categorized by <80% and 80% - 100% and summarized by treatment group. In addition, compliance during last week before the actual DBPCFC will be summarized as <45% and 45% - 100%

### **2.4.2 Prior, concomitant and post therapies**

Concomitant medications and significant non-drug therapies prior to and after the start of study treatment will be summarized according to the Anatomical Therapeutic Chemical (ATC) classification system, and preferred term by treatment arm. Any allergy related medications taken during the study treatment period will be listed separately.

## 2.5 Analysis supporting primary objective(s)

The primary objective of this study is to characterize the dose-response relationship between remibrutinib treatment after one month of treatment (CCI [REDACTED]) and placebo with respect to the responder rate as the primary endpoint. The consecutive steps are therefore (1) to confirm an overall dose response signal, (2) to estimate the dose-response curve to support selecting dose(s) for the Phase 3 studies. The Multiple Comparison Procedures – Modeling (MCP-Mod) methodology (Bretz et al 2005) will be used to address these goals.

CCI [REDACTED]

[REDACTED] final analysis will be performed upon end of study.

### 2.5.1 Primary endpoint(s)

The primary endpoint is responder rate, where responder rate is defined as the proportion of participants tolerating a single dose of  $\geq 600$  mg (1044 mg cumulative tolerated dose) of peanut protein without dose-limiting symptoms during the DBPCFC conducted after one month of study treatment.

### 2.5.2 Statistical hypothesis, model, and method of analysis

CCI [REDACTED]

#### Primary endpoint – Responder rate

The statistical analysis will be based on the PD analysis set.

The null hypothesis of a no dose-response relationship for responder rate will be tested at a significance level of 10% against the one-sided alternative hypothesis of a dose-response relationship using the MCP-Mod methodology (Bretz et al 2005, Pinheiro et al 2014).

The primary endpoint will be analyzed based on logistic regression model, including treatment arm as a categorical variable (all remibrutinib doses and placebo) and including, but not limited to, log-transformed baseline total IgE and baseline tolerated peanut allergen dose as covariates. The logistic regression model is defined as follows. The response  $y_{ij}$  for subject  $i$  in dose group  $j$  receiving dose  $d_j$  is modelled as  $y_{ij} \sim \text{Bin}(1, p_{ij})$  with  $p_{ij} = \text{logit}^{-1}(\delta_j + x_{ij}^T \beta)$ , where  $x_{ij}$  are covariates of subject  $i$  in dose group  $j$ ,  $\delta_j$  are dose-specific intercepts and  $\beta$  are parameters associated with the covariates, common across dose groups. Any missing values in the covariates will be replaced with the median value for that variable. All covariates will be standardized to have a mean of 0 and a standard deviation of 0.5, so they are on the same scale as the binary input (Gelman, 2008).

In case of complete separation, the Maximum Likelihood estimate of the logistic regression does not exist. If this problem is encountered, we will replace the logistic regression by a Bayesian logistic regression with weakly informative priors. The Bayesian logistic regression model follows the same model equation as above, but incorporates weakly informative priors for the model's parameters. Priors are specified as follows: for parameters associated to the

treatment arm,  $\delta_j$ , a student-t distribution with a mean of 0, standard deviation of 2, and 5 degrees of freedom is employed. This choice of prior, conveys some information through its 0 mean while having a large variance (considering that the model parameters are on logit scale) to allow the data to dominate the posterior distribution. For parameters associated with the remaining standardized covariates, a normal prior is chosen with a mean of 0 and standard deviation of 2, indicating a lack of strong prior beliefs or specific information about these parameters. The Bayesian logistic regression model is fitted with the `brms` package on R 4.3.1, using the adaptive Hamiltonian Monte Carlo (HMC) sampler (Carpenter, et al., 2017) with 4 chains for 3,000 iterations including 500 iterations of warm-up. Convergence of the HMC will be assessed using the following diagnostics: the trace plot, the lower number of effective sample size and the highest R hat value.

Odds ratio and 80% confidence intervals (CI) will be presented comparing each remibrutinib dose to placebo with respect to the proportions of response. Similarly, marginal difference in response proportions will also be presented. If frequentist method will be used, marginal difference in responder rates with one-sided p-value and corresponding 80% CI will be estimated from the logistic regression model using the methodology described in (Ge, et al., 2011) with sandwich variance estimator (Liu & Xi, 2024). If Bayesian method will be used, marginal difference in responder rates with posterior probability of marginal difference above 0, and 80% credible interval will be provided. The posterior distribution of the marginal difference in response probabilities between dose group  $j$  and placebo (i.e., Dose=0) will be obtained based on the following formula:

$$\begin{aligned} & \frac{1}{n} \sum_{i=1}^n P(Y = 1 | Dose = j, X_i = x_i^T) - \frac{1}{n} \sum_{i=1}^n P(Y = 1 | Dose = 0, X_i = x_i^T) \\ &= \frac{1}{n} \sum_{i=1}^n \text{logit}^{-1}(\delta_j + x_i^T \beta) - \frac{1}{n} \sum_{i=1}^n \text{logit}^{-1}(\delta_0 + x_i^T \beta) \end{aligned}$$

Where

- $Y = 1$  represents responder
- $n$  is the total number of participants in the study
- $x_i^T$  are covariates of subject  $i$
- $\delta_j$  are dose-specific intercepts ( $j = 0$  corresponding to placebo)

$\beta$  are parameters associated with the covariates, common across dose groups. With a MCMC sample from the posterior distribution for  $\delta_j$ ,  $\delta_0$ ,  $\beta$ , the posterior distribution for the mean difference in marginal response rates can be derived as well as the posterior mean and 80% credible interval and the probability of marginal differences above 0 could be derived.

Generalized MCP-Mod (Pinheiro et al 2014) will be applied based on the estimates and SE of the proportion of responders from the frequentist logistic regression model. The CCI 1-week treatment regimen will not be included in the dose response model fit. To perform generalized MCP-Mod trend test, the adjusted values of the proportion of responders for remibrutinib versus

placebo arm and associated covariance matrix will be obtained from the model. If the Bayesian logistic regression is used, we will adopt the Bayesian MCP-Mod framework proposed by (Fleischer, et al., 2022). To perform the Bayesian MCP step, we use the optimal contrast vectors calculated from the regular MCP-Mod that is, ignoring any information from the prior. For each model shape, the posterior probability will be calculated such that the underlying contrast is greater than 0. The Bayesian Mod step follows the same procedure as the frequentist Mod Step, except that MCMC samples are used instead of bootstrap samples.

For each candidate model a contrast test statistic, based on a linear combination of the treatment estimates per dose will be derived. The contrast coefficients will be chosen to maximize the power to detect pre-specified candidate models. For that purpose, beta model,  $E_{\max}$  and sigmoid  $E_{\max}$  dose-response shapes will be selected. For the  $E_{\max}$  model ( $E_0 + E_{\max} * d / (d + ED_{50})$ ), two shapes with  $ED_{50} = \text{CCI}$  will be used, while for the sigmoid  $E_{\max}$  model ( $E_0 + E_{\max} * d^h / (d^h + ED_{50}^h)$ ) two shapes with  $(ED_{50}, h) = (\text{CCI}, 1)$  and  $(\text{CCI}, 2)$  will be utilized, where  $E_0$  is the expected placebo effect,  $E_{\max}$  is the maximum change in effect over placebo,  $ED_{50}$  is the dose at which 50% of  $E_{\max}$  is achieved and  $h$  is Hill parameter, and a betamod  $f(d, \theta) = E_0 + E_{\max} B(\delta_1, \delta_2)(d/\text{scal})^{\delta_1} (1 - d/\text{scal})^{\delta_2}$  shape with  $(\text{scale}, \delta_1, \delta_2) = (\text{CCI}, 1, 1)$  to capture the nonmonotone dose-response relationship (Figure 2-1).

Figure 2-1

CCI

CCI

Optimal contrasts will be derived for the remibrutinib CCI dose regimen dose-response curves according to the model shapes above .

The global test decision is based on the maximum of all contrast test statistics from the proposed candidate shapes. A critical value  $q$  controlling the type I error rate can be derived from the fact that the contrast test statistics approximately follow an asymptotic multivariate normal distribution. If the maximum contrast test statistic exceeds the critical value  $q$ , the overall null

hypothesis of a constant dose-response curve is rejected and proceeds to the estimation steps to determine the dose-response curve.

### **Dose response curve and target dose estimation (dose-finding step)**

Once statistically significant dose-response relationship is established, the dose-response modeling will be performed with a combination of bootstrapping and model averaging based on the choice of candidate models.

Dose-response estimation for a sigmoid  $E_{\max}$  or beta model, if selected, will be fit by fixing the **CCI** for the sigmoid  $E_{\max}$  model, and fixing the location of the maximum effect for the beta model (keeping the ratio  $\delta_1/(\delta_1+\delta_2)$  fixed).

As different models contribute to the bootstrap resamples, the approach can be considered more robust than simple model selection (Schorning et al 2016) in the generalized MCP-Mod framework.

First, we draw bootstrap samples repeated 10000 times from the multivariate normal distribution of the estimates originating from the first-stage model. Next, for each bootstrapped data set we fit our candidate models, select the one with lowest AIC and save the corresponding estimated quantities of interest. This selection step implies that the bootstrap samples potentially come from different models.

Median from all the bootstrapped means and confidence limits for each dose-level around model-averaged predictions will be obtained using a non-parametric bootstrap procedure repeated at least 10,000 times.

Results of the model-averaged analysis will be presented for each dose, including the placebo-adjusted estimates of the responder rate and its associated 80% CI.

### **2.5.3 Handling of intercurrent events**

The primary analysis will account for different intercurrent events as described below.

1. The primary analysis will be performed with completers only assuming dropouts occur completely at random. A completer is defined as a participant who completes DBPCFC after one month of study treatment or three weeks of placebo plus one week of study treatment. In other words, treatment policy strategy is applied here. Missing outcomes due to treatment discontinuation/interruption are assumed to occur at random and ignored.
2. Intake of rescue medication prior to DBPCFC conducted before one month: ignorable (treatment policy strategy, reflected in the Treatment attribute)

### **2.5.4 Sensitivity analyses**

To show treatment effect without the benefit of prohibited medications as a sensitivity analysis, the primary analysis will be repeated with DBPCFC results took after the relevant use of prohibited medication (i.e., having protocol deviation coded as COMD01 – participant took prohibited medication mentioned in Protocol V2 Table 6-4 or took medication that was not allowed under certain conditions during study mentioned in Protocol V2 Table 6-2) being treated as missing values.

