## 6.2.2 Prohibited medication

Use of the treatments displayed below ([Table 6-4](#)) is not allowed from Screening Visit 1 to the completion of all three end-of-treatment visits (Day 28). The minimum required period without prohibited treatment before Screening Visit 1 is also shown.

If a participant develops a medical condition that requires use of prohibited treatment or if participant exhibits a behavior of non-compliance regarding prohibited medications at any timepoint from Screening Visit 1 to the end of the completion of all three end-of-treatment visits (Day 28), investigational treatment and DBPCFC must be discontinued (see also [Section 9.1.1](#)).

As described above, remibrutinib is metabolized mainly by CYP3A4. Therefore, concomitant administration of remibrutinib with drugs that are strong and moderate CYP3A4 inhibitors is prohibited to avoid increases in the systemic exposure up to 4-fold. Although no DDI study has been conducted so far with CYP3A4 inducers, likewise, concomitant administration of remibrutinib with drugs that are moderate and strong CYP3A4 inducers is prohibited as a published SimCYP model predicts a 90% decrease in remibrutinib blood exposure which can lead to a total loss of efficacy.

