#### **12.4.4 Handling of missing values not related to intercurrent event**

#### **12.4.5 Sensitivity analyses**

Not applicable.

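### The prohibited-medication sensitivity analysis (SAP 2.5.4) deletes failed challenges along with passed ones, so it holds only if users would have responded like non-users; a non-responder bound for symptom-masking drugs should be added

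*SAP*

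**What the plan says.** SAP 2.5.4 contains the only analysis that either document labels as a sensitivity analysis of the primary endpoint; Protocol 12.4.5 states that none applies. Its purpose is given as "To show treatment effect without the benefit of prohibited medications as a sensitivity analysis". The method is that "the primary analysis will be repeated with DBPCFC results took after the relevant use of prohibited medication" (deviation code COMD01, covering Protocol Table 6-4 and breaches of the Table 6-2 conditions) "being treated as missing values". Nothing separates passed from failed challenges, and the word relevant is not defined.

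SAP 2.5.3 determines what missing then means: "The primary analysis will be performed with completers only assuming dropouts occur completely at random", and missing outcomes after treatment discontinuation or interruption "are assumed to occur at random and ignored". Nothing is imputed, so a result set to missing leaves the analysis.

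Protocol Table 6-2 keeps antihistamines, short-acting beta agonists and H2 antagonists away from the challenge for stated periods. Protocol 6.2.2 prohibits moderate and strong CYP3A4 inhibitors because exposure could rise up to 4-fold. It prohibits inducers because "a published SimCYP model predicts a 90% decrease in remibrutinib blood exposure which can lead to a total loss of efficacy". The same section says that after prohibited treatment "investigational treatment and DBPCFC must be discontinued".

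**The concern.** The purpose is to remove a benefit. If a drug can only mask symptoms, taking its benefit away can turn a pass into a failure but cannot turn a failure into a pass. The observed responder rate in an arm should therefore be a ceiling. Deleting results whatever their outcome does not respect that ceiling, because a known non-response leaves the denominator.

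COMD01 also pools drugs that act in different ways. Symptom-masking drugs can help in any arm. CYP3A4 inhibitors and inducers act only through remibrutinib exposure. For inducers there is no benefit to remove, and deleting a failure after an inducer takes away a possible harm to remibrutinib.

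At stake is whether a check meant to be stricter than the primary analysis can come out more favourable, in arms where one participant is worth several percentage points.

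**Working it through.** **Denominators.** Protocol 12.8 gives 72 participants, allocation 2:2:2:1:1 and about 10% discontinuation.
- One-month arm: 72 × 2/8 × 0.90 = 16.2
- Placebo arm: 72 × 1/8 × 0.90 = 8.1

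These reproduce the upper ends of the stated 14 to 16 and 7 to 8 completers. The lower ends, 14 and 7, are those used for power; they imply a loss of 1 − 14/18 = 22%. The MCP-Mod power cannot be recomputed because doses, shapes and the placebo rate are redacted, but this point does not need it.

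**Assumptions.**
- Remibrutinib: 11/14, close to the 80% in the Amendment 02 rationale.
- Placebo: 0/7 to 1/7. The design value is redacted; the visible rows of SAP Table 2-2 pool to (0 + 7)/(26 + 138) = 4.3%.
- Number of COMD01 challenges: one or two in an arm, as illustration only.
- All figures are crude proportions, not the covariate-adjusted model.

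**Within one remibrutinib arm, users of a symptom-masking drug.** If the drug can only help, the drug-free rate lies between all users counted as non-responders (lower) and the observed rate (upper).

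| Users in the arm | Lower bound | Observed (upper) | Deletion | Deletion within bounds? |
|---|---|---|---|---|
| 1 failed | 11/14 = 78.6% | 11/14 = 78.6% | 11/13 = 84.6% | No, 6.0 points above |
| 2 failed | 11/14 = 78.6% | 11/14 = 78.6% | 11/12 = 91.7% | No, 13.1 points above |
| 1 failed, 1 passed | 10/14 = 71.4% | 11/14 = 78.6% | 10/12 = 83.3% | No, 4.8 points above |
| 1 passed | 10/14 = 71.4% | 11/14 = 78.6% | 10/13 = 76.9% | Yes |

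With 13/16, deleting one failure gives 13/15: 81.2% becomes 86.7%, or +5.4 points.

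**Difference from placebo.** Base: 11/14 − 1/7 = 64.3 points.
- Delete one remibrutinib failure: 11/13 − 1/7 = 70.3 (+6.0).
- Delete one remibrutinib responder: 10/13 − 1/7 = 62.6 (−1.6).
- Delete one placebo failure: 11/14 − 1/6 = 61.9 (−2.4). With placebo at 0/7 the change is 0.
- Delete one failure in each arm: 11/13 − 1/6 = 67.9 (+3.7). With placebo at 0/7 it is +6.0.
- One remibrutinib failure and one remibrutinib pass among users: deletion gives 10/12 − 1/7 = 69.0 (+4.8). Counting both as non-responders gives 10/14 − 1/7 = 57.1 (−7.1). The two rules move in opposite directions and end 11.9 points apart.

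**Expected shift from deletion in one arm** = m × (p_non-user − p_user without the drug), where m is the share of users. With 80% among non-users:
- m = 10%, users 40%: 0.10 × (0.80 − 0.40) = +4 points; m = 20% gives +8.
- Users 80%: 0.
- m = 10%, users 90%: −1 point.

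**The case against.** Deletion has a real rationale. Protocol 6.2.2 says that the challenge should not take place after prohibited treatment, so setting such a result to missing restores the data the protocol intended. It also matches SAP Table 2-1, which sets invalid challenges (TRT12, OTH20, OTH24) to missing whatever their result. This stands for Table 6-4 drugs; it is weaker for timing breaches of Table 6-2.

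A reader might infer that the analysis cannot show the drug-free effect at all. The documents do not support that. Deletion does estimate it if users would have responded like non-users, and SAP 2.5.3 already declares a completely-at-random assumption for the primary analysis. The defect is that this check rests on the assumption without testing it.

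A reader might also treat 10/13 against 10/14 (76.9% against 71.4%) as showing that deletion is 5.5 points too favourable after an assisted pass. That takes non-response as the truth. The participant might have passed unaided: at an 80% rate the expected drug-free value is (10 + 0.8)/14 = 77.1%, which deletion nearly matches. Counting passes as non-response is a bound, not a better estimate.

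The gap is also narrower than it may seem. Users managed as Protocol 6.2.2 requires have no challenge, and supplementary estimand 2 then counts them as non-responders unless a public health emergency is the cause. Estimand 4 and the Bayesian analysis with historical placebo data also examine the primary result. None of these, however, addresses users who were challenged anyway, and estimands 1 and 3 will not be run.

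**Conclusion.** The concern holds in a limited form. The planned sensitivity analysis depends on an untested assumption, and deleting failures that occurred despite a symptom-masking drug can push a remibrutinib arm above the rate that should be its ceiling. With 11/14 or 13/16 responders, one such deletion is worth 5.4 to 6.0 points and two of 14 are worth 13.1.

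Two stronger readings should be resisted. The analysis is not shown to favour remibrutinib: the shift can go either way, and neither the number nor the outcomes of COMD01 challenges are given. Nor does it delete every challenge after a prohibited drug, since the SAP limits it to relevant use, although that term is undefined. With placebo response near zero, deleting placebo failures changes little, so offsetting between arms is weak; that is a tendency under an assumed placebo rate.

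The bounds assume that a masking drug never worsens the challenge result. The primary analysis retains these results and is not affected. This is a cheap improvement to a secondary check.

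**What to change.** In SAP 2.5.4, before unblinding:
1. Define relevant use, and classify each COMD01 case blinded to treatment arm and, if possible, to challenge result.
2. For symptom-masking medication taken too close to the peanut challenge, run the sensitivity analysis with those participants as non-responders: failures stay failures and passes are not credited. Present it as a lower bound for each arm's rate, beside the primary analysis (upper bound within each arm) and the planned deletion analysis. These are bounds on arm rates. For the difference, the most conservative pairing is the remibrutinib lower bound with the placebo upper bound.
3. Do not apply the non-responder rule to CYP3A4 inhibitors or inducers. For inducers, keep the observed results in this analysis and list the participants. List inhibitor users separately as well; the deletion analysis already shows the result without them. State how other Table 6-2 breaches, such as immunotherapy timing, are classed, and how overlaps are resolved: cimetidine appears in both Table 6-2 and Table 16-8.
4. Report COMD01 counts by arm, drug class and challenge outcome.

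The cost is SAP wording, a small blinded review and one additional output. The added result is deliberately conservative and may look slightly less favourable.
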